10.8. Appendix 8: CDC Classification for HIV-1 Infection

Note that the CD4+ T-lymphocyte count takes precedence over the CD4+ T-lymphocyte percentage in HIV infection stages 1, 2, and 3. The CD4+ T-lymphocyte percentage should only be considered if the count is missing.

HIV infection, stage 0

Indicates early HIV infection, inferred from a negative or indeterminate HIV test result within 180 days of a positive result. The criteria for stage 0 supersede and are independent of criteria used for other stages.

HIV infection, stage 1

Laboratory confirmation of HIV infection with no AIDS-defining condition, and

- CD4+ T-lymphocyte count of ≥ 500 cells/ μ L, or
- CD4+ T-lymphocyte percentage of total lymphocytes of $\geq 26\%$.

HIV infection, stage 2

Laboratory confirmation of HIV infection with no AIDS-defining condition, and

- CD4+ T-lymphocyte count of 200 to 499 cells/ μ L, or
- CD4+ T-lymphocyte percentage of total lymphocytes of 14% to 25%.

HIV infection, stage 3 (AIDS)

Laboratory confirmation of HIV infection, and

- CD4+ T-lymphocyte count of < 200 cells/ μ L, or
- CD4+ T-lymphocyte percentage of total lymphocytes of $< 14\%$, or
- Documentation of an AIDS-defining condition (see below).

Documentation of an AIDS-defining condition supersedes a CD4+ T-lymphocyte count of > 200 cells/ μ L and a CD4+ T-lymphocyte percentage of total lymphocytes of $> 14\%$.

HIV infection, stage unknown

Laboratory confirmation of HIV infection, and

- No information on CD4+ T-lymphocyte count or percentage, and
- No information on presence of AIDS-defining conditions.

Stage-3-defining opportunistic illnesses in HIV infection

- Candidiasis of bronchi, trachea, or lungs
- Candidiasis of oesophagus

- Cervical cancer, invasive
- Coccidioidomycosis, disseminated or extrapulmonary
- Cryptococcosis, extrapulmonary
- Cryptosporidiosis, chronic intestinal (>1 month's duration)
- Cytomegalovirus disease (other than liver, spleen, or nodes), onset at age >1 month
- Cytomegalovirus retinitis (with loss of vision)
- Encephalopathy, HIV-related
- Herpes simplex: chronic ulcers (>1 month's duration) or bronchitis, pneumonitis, or oesophagitis (onset at age >1 month)
- Histoplasmosis, disseminated or extrapulmonary
- Isosporiasis, chronic intestinal (>1 month's duration)
- Kaposi's sarcoma
- Lymphoma, Burkitt's (or equivalent term)
- Lymphoma, immunoblastic (or equivalent term)
- Lymphoma, primary, of brain
- Mycobacterium avium complex or Mycobacterium kansasii, disseminated or extrapulmonary
- Mycobacterium tuberculosis of any site, pulmonary, disseminated or extrapulmonary
- Mycobacterium, other species or unidentified species, disseminated or extrapulmonary
- Pneumocystis jirovecii pneumonia
- Pneumonia, recurrent
- Progressive multifocal leukoencephalopathy
- Salmonella septicaemia, recurrent
- Toxoplasmosis of brain, onset at age >1 month
- Wasting syndrome attributed to HIV.

Source: [CDC, 2014]

10.9. Appendix 9: Permissible Procedures During COVID-19 Pandemic

Overall Rationale for this Appendix

COVID-19 pandemic may impact the conduct of clinical studies. Challenges may arise from quarantines, site closures, travel limitations, interruptions to the supply chain for the study intervention or other considerations if site personnel or study participants become infected with COVID-19. These challenges may lead to difficulties in meeting protocol-specified procedures, including administering or using the study intervention or adhering to protocol-mandated visits and laboratory/diagnostic testing.

This protocol appendix outlines measures that may be applicable for any site impacted by the COVID-19 pandemic. The purpose of the appendix is to provide information on the measures to be taken to protect participants' safety, welfare and rights, and promote data integrity.

These measures will remain in place until the site is able to resume normal working activities and may be re-instated as warranted.

Study Procedures During COVID-19 Pandemic

During the special circumstances caused by the current COVID-19 pandemic, the investigator should consider specific public health guidance, the impact of any travel restrictions implemented by local/regional health authorities and local institutions, and individual benefit /risk when making enrollment and treatment decisions for trial participants.

Every effort should be made to adhere to protocol-specified assessments for participants on study intervention, including follow up however when not possible, for the duration of these special circumstances, the following measures may be implemented for enrolled participants.

- Investigators should document in site files how restrictions related to COVID-19 led to the changes in study conduct and duration of those changes and indicate which trial participants were impacted and how those trial participants were impacted (as per the current local COVID-19 related regulatory guidance).
- Missing protocol required data/visits due to COVID-19 should be noted in participant notes and recorded as a COVID-19 protocol deviation.
- Participants previously deemed eligible during the screening period unable to attend within the allowable screening window due to COVID-19 may be rescreened.
- A participant who is found to have SARS-CoV-2 infection during the study may proceed in the study at the discretion of the investigator and sponsor assuming the participant isolates according to current Centers for Disease Control and Prevention guidance and then has a repeat SARS-CoV-2 test that is negative.

- Participants who are withdrawn from the study due to COVID-19 infection (including exposure to COVID-19) may be replaced based upon the discretion of the sponsor and investigator.

Vaccination for SARS-CoV-2

Vaccination with an approved vaccine for SARS-CoV-2 is not permitted during the study but may occur at least 14 days prior to dosing on Day 1 or after Day 39/Early Discontinuation Visit.

Data Management/Monitoring:

- If on-site monitoring is no longer permitted, VH/GSK will consider remote Source Data Verification/Source Document Review (SDV/SDR) where permitted by the clinical site/institution. Remote SDV/SDR will be proposed to study sites to meet a patient and/or critical quality need, e.g., to assess participant safety or to ensure data integrity. In case of remote SDV/SDR, VH/GSK will work with the site to ensure participant privacy.
- eCRF/CRF Final or Interim Sign off Process: The investigator is responsible for ensuring that the data within the eCRF casebook and any other data sources utilized during the study for each study participant is complete and consistent with source documents throughout the study (ICH GCP 4.9.1 4.9.2). The investigator may sign/re-sign the eCRF from any computer/location by accessing the eCRF using his/her unique eCRF log-in credentials. The investigator may delegate this activity to another medically qualified and trained sub-investigator and this must be documented on the Delegation of Responsibilities (DoR) Log. It is recommended that the PI identifies a sub-investigator as a back-up for eCRF signatures. The sub-investigator must be appropriately trained on the protocol and eCRF requirements (with training documented), and the DoR log updated accordingly.
- Essential Document Sign Off Process: If an investigator is unable to print and sign essential documents such as Protocol /Amendment signature page then Email approval can be accepted by replying to the relevant email that is sent by VH/GSK.

10.10. Appendix 10: Country-specific requirements

10.10.1. Specific requirements for France

This appendix includes all applicable requirements of French Public Health Code / specific local GSK requirements and identifies, item per item, the mandatory modifications or additional information to the study protocol.

1. Concerning the «SELECTION OF STUDY POPULATION AND WITHDRAWAL CRITERIA»

The following vulnerable subject populations will be excluded of compensation for the inconvenience of participating in the study: minors, protected subjects, adult subjects not in condition to express their consent, subjects deprived of liberty, subjects receiving psychiatric cares, subjects hospitalized in a Health and Social Establishment for other purpose than the participation to the study.

A subject will be eligible for inclusion in this study if he /she is either affiliated to or beneficiary of a social security category (French Public Health Code L.1124-1).

It is the investigator's responsibility to ensure and to document (in the source document - subject notes) that the subject is affiliated to or beneficiary of a social security category.

Subjects will be compensated for the inconvenience of participating in the study. The amount of compensation is stated in the Informed Consent Form. Subjects not completing the study for whatever reason could be compensated generally on a pro rata basis.

According to French Public Health Code (L.1121-16 and R.1121-16), the following people must be registered in National File ("Fichier National"):

- Healthy volunteer;
- Subjects if the aim of the study is not linked to their disease;
- Subjects on request of the Ethics Committee regarding study risks and constraints.

The following details will be described:

- Reference of the study
- Surname and first name
- Date and place of birth
- Gender
- Dates of beginning and termination of the study
- Exclusion period during which the subject cannot participate to another study (French Public Health Code L.1121-12)

- The total amount of compensation, if any.

The subjects' registration in National File ("Fichier National") should be documented in the source document - subject notes and monitored by the CRA.

2. Concerning the "STUDY GOVERNANCE CONSIDERATIONS"

- **In section "Regulatory and Ethical Considerations, including the Informed Consent Process" of study protocol**

⇒ Concerning **the process for informing the subject** and/or his/her legally authorized representative, the following text is added:

French Patient Informed Consent is a document which summarizes the main features of the study and allows collection of the subject and/or his/her legally authorized representative written consent. It also contains a reference to the single scientific and ethical regulatory authorization.

⇒ **Concerning the management of the Patient Informed Consent Forms**, the following text is added:

French Patient Informed Consent Form is in duplicate (triplicate for minor subject).

The first page of the Patient Informed Consent Form is given to the investigator. The copy is kept by the patient or legally authorized representative.

- **Notification to the hospital director**

In accordance with Article R.1123-69 of the French Public Health Code, the Hospital Director is informed of the commitment to the trial in her/his establishment. The Hospital Director is supplied with the protocol and any information needed for the financial disposition, the name of the investigator(s), the number of sites involved in his establishment and the estimated time schedule of the trial.

- **Information to the hospital pharmacist**

In accordance with Article R.1123-70 of the French Public Health Code, the Hospital Pharmacist is informed of the commitment to the trial in her/his establishment. The Pharmacist is supplied with a copy of the protocol (which allows her/him to dispense the drug(s) of the trial according to the trial methodology), all information concerning the product(s) of the trial (e.g., included in the IB), the name of the investigator(s), the number of sites involved in her/his establishment and the estimated time schedule of the trial.

3. Concerning the “DATA MANAGEMENT” the following text is added:

Within the framework of this clinical trial, data regarding the identity of the investigators and/or co-investigators and/or the pharmacists if applicable, involved in this clinical trial, and data regarding the subjects recruited in this clinical trial (subject number, treatment number, subjects status with respect to the clinical trial, dates of visit, medical data) will be collected and computerized in VH/GSK data bases by VH/GSK or on its behalf, for reasons of follow up, clinical trial management and using the results of said clinical trial. According to the data privacy regulation, each of these people aforesaid has a right of access, correction and opposition on their own data through VH/GSK (Clinical Operations Department).

- **Ethnic Origin**

In accordance with the data privacy regulation, the ethnic origin, as any personal data, can only be collected if the collection of this data is strictly necessary and relevant for the purpose of the study.

- **Testing of Biological Samples**

In accordance with the French Public Health Code – article L1211-2, a biological sample without identified purpose at the time of the sample and subject's preliminary information is not authorized.

4. Concerning Data Privacy

In accordance with the applicable data privacy regulation, personal data are processed in a manner that ensures appropriate security, including protection against unauthorized or unlawful processing and against accidental loss, destruction or damage, using appropriate technical or organizational measures. The processing is whether deemed to be compliant with one of the methodology of reference (**MR-001**) or has been the subject of a request for authorization to the CNIL. The investigator has, regarding the processing data related to her/him, a right of access, of rectification, erasure and of opposition with VH/GSK in accordance with the legal provisions.

1. INTRODUCTION

The purpose of this SAP is to describe the planned analyses to be included in the CSR for Study 218307. Details of the planned End of Study analyses are provided. Selected End of Study outputs will also be provided at the planned Interim analyses (see also Section 4.7). See OPS for the list of outputs delivered at Interim and End of Study analyses.

1.1. Objectives, Estimands and Endpoints

Objectives	Endpoints
Primary	
To evaluate the antiviral activity of orally administered VH4004280 and VH4011499 monotherapy over 10 days in HIV-1 infected Treatment-Naïve (TN) participants	Maximum change from baseline (Day 1) in plasma HIV-1 ribonucleic acid (RNA) through Day 11.
Secondary	
To assess the safety and tolerability of orally administered VH4004280 and VH4011499	
 • Incidence of adverse events (AEs), severity of AEs and AEs leading to study treatment discontinuation • Change from baseline and maximum toxicity grade increase from baseline for liver panel laboratory parameters (consisting of total and direct bilirubin, ALT, ALP and AST)
To characterize the pharmacokinetic profiles of orally administered VH4004280 and VH4011499	PK measures that include but are not limited to: 
 • Maximum observed plasma drug concentration (Cmax), • Time to maximum observed plasma drug concentration (tmax), • Concentrations on Day 11 for VH4004280 and VH4011499
To determine the relationship between the exposure levels of orally administered VH4004280 and VH4011499 and change in plasma HIV-1 RNA	VH4004280 and VH4011499 PK parameters with maximum change in plasma HIV-1 RNA from baseline through Day 11

CCI

1.1.1. Estimands

Table 1 Estimands Definitions

Endpoints	Estimand			
	Population	Treatment	Summary Measure	Intercurrent event (IE) / strategy / rationale
Primary Objective: To evaluate the antiviral activity of orally administered VH4004280 and VH4011499 monotherapy over 10 days in HIV-1 infected Treatment-Naïve (TN) participants				
Maximum change from baseline (Day 1) in plasma HIV-1 ribonucleic acid (RNA) through Day 11.	Overtly healthy (other than HIV-1 infection) treatment naïve individuals	VH4004280 or placebo single dose on Day 1, or VH4011499 or placebo single dose on Day 1 and Day 6	Mean of maximum change from Baseline in log10 HIV-1 RNA during Days 1-11	
Discontinuation of study treatment due to any reason: Treatment policy strategy, i.e., any HIV-1 RNA data available after study treatment discontinuation day + 1 and prior to starting SoC will be used in calculation of max VLD
 
Use of SoC medication prior to Day 11: While on-treatment strategy, i.e., HIV-1 RNA collected after initiation of SoC, if for any reason this takes place prior to Day 11 will be excluded from calculation of max VLD
 
Use of prohibited medication: Treatment policy strategy, i.e., any HIV-1 RNA data available after use of prohibited medication will be used in calculation of max VLD
 
Missed or incorrect doses of study treatment: Treatment policy strategy, i.e., HIV-1 RNA collected after missed or incorrect dose(s) will be used in calculation of max VLD
 
Rationale: Interest is in evaluating efficacy irrespective of study treatment discontinuation or missed/incorrect doses, or use of prohibited medications, hence a treatment policy strategy is appropriate. Also, interest is to evaluate efficacy of VH4004280/VH4011499 monotherapy and not in combination with

Endpoints	Estimand			
	Population	Treatment	Summary Measure	Intercurrent event (IE) / strategy / rationale
				
other antiretroviral medication hence a while on-treatment strategy is appropriate.
 
Note: discontinuation or missed doses of VH4004280 is not possible as only a single dose on Day 1 is administered, hence these IEs apply only to VH4011499 and to placebo matched for VH4011499.

Secondary Objective: To assess the safety and tolerability of orally administered VH4004280 and VH4011499				

 Incidence of adverse events (AEs), severity of AEs and AEs leading to study treatment discontinuation Change from baseline and maximum toxicity grade increase from baseline for liver panel laboratory parameters 	
Overtly healthy (other than HIV-1 infection) treatment naïve individuals
	
VH4004280 or placebo [REDACTED] [REDACTED] or [REDACTED] [REDACTED] or VH4011499 or placebo [REDACTED] [REDACTED]
	
 AEs: 
 Number and percentage of participants with AEs Number and percentage of participants with AEs by severity grade Number and percentage of participants with AEs leading to study treatment discontinuation Liver panel laboratory parameters 
 Summaries (mean, median, std, Q1, Q2, min, max) of change from baseline in liver 	
Discontinuation of study treatment: Treatment policy strategy, i.e., all data to be used regardless of whether the study treatment discontinuation has occurred
 
Use of SoC medication prior to Day 11: While on-treatment strategy, i.e., Safety data collected after initiation of SoC, if for any reason this takes place prior to Day 11 will be excluded from monotherapy Safety summaries
 
Use of prohibited medication: Treatment policy strategy, i.e., all data to be used regardless of whether prohibited medication has been used
 
Rationale: There is interest in evaluating and reporting monotherapy safety events from the monotherapy period and regardless of whether participants have completed monotherapy treatment or received prohibited medication
 
Note: discontinuation of VH4004280 treatment is not possible as only a single dose on Day 1 is administered, hence this IE applies only to VH4011499 and to placebo matched for VH4011499.

CONFIDENTIAL

218307

[figure not shown]
Endpoints	Estimand			
	Population	Treatment	Summary Measure	Intercurrent event (IE) / strategy / rationale
			
 panel laboratory parameters ○ Number and percentage of participants with maximum grade toxicity relative to Baseline 	
Secondary Objective: To characterize the pharmacokinetic profiles of orally administered VH4004280 and VH4011499				
Concentration on Day 11 and PK parameters including 
 ○ Cmax ○ tmax 	Overtly healthy (other than HIV-1 infection) treatment naïve individuals	VH4004280 or placebo CCI [REDACTED] [REDACTED], or VH4011499 or placebo CCI [REDACTED] [REDACTED] [REDACTED]	Summary statistics (e.g., arithmetic mean, median, std, minimum, maximum, geometric mean, sd (log), %CVb)	
Discontinuation of monotherapy treatment with VH4011499: While on-treatment strategy, i.e., concentration values after study treatment discontinuation day + 1 will be excluded from analysis
 
Use of prohibited medication: treatment policy strategy, i.e., all PK data to be used regardless of whether prohibited medication was used
 
Rationale: Discontinuation of VH4011499 treatment may bias the evaluation of Pharmacokinetic behavior of VH4011499 as expected during and after the end of 10 days monotherapy period
 
Note: discontinuation of VH4004280 treatment is not possible as only a single dose on Day 1 is administered

CCI				

CONFIDENTIAL

218307

Endpoints CCI	Estimand			
	Population	Treatment	Summary Measure	Intercurrent event (IE) / strategy / rationale

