• Maximum change from baseline (Day 1) in plasma HIV-1 ribonucleic acid (RNA) through Day 11.	Overtly healthy (other than HIV-1 infection) treatment naïve individuals	VH4004280 or placebo single dose on Day 1 or VH4011499 or placebo single dose on Day 1 and Day 6	Mean of maximum change from Baseline in log10 HIV-1 RNA during Days 1-11	
Discontinuation of study treatment due to any reason: Treatment policy strategy, i.e., any HIV-1 RNA data available after study treatment discontinuation day + 1 and prior to starting SOC will be used in calculation of max VLD
 
Use of SOC medication prior to Day 11: While on-treatment strategy, i.e., HIV-1 RNA collected after initiation of SoC, if for any reason this takes place prior to Day 11 will be excluded from calculation of max VLD
 
Use of prohibited medication: Treatment policy strategy, i.e., any HIV-1 RNA data available after use of prohibited medication will be used in calculation of max VLD
 
Missed or partial doses of study treatment: Treatment policy strategy, i.e., HIV-1 RNA collected after missed or partial dose(s) will be used in calculation of max VLD
 
Rationale: Interest is in evaluating efficacy irrespective of study treatment discontinuation or missed/partial doses, or use of prohibited medications, hence a treatment policy strategy is appropriate. Also, interest is to evaluate efficacy of VH4004280/VH4011499 monotherapy and not in combination with other antiretroviral medication hence a while on-treatment strategy is appropriate.
 
Note: discontinuation or missed or partial doses of VH4004280 is not possible as only a single dose on Day 1 is administered, hence these IEs apply only to VH4011499 and to placebo matched for VH4011499.

Secondary Objective: To assess the safety and tolerability of orally administered VH4004280 and VH4011499				

Endpoints	Estimand			
	Population	Treatment	Summary Measure	Intercurrent event (IE) / strategy / rationale

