5.1. Inclusion Criteria

Entry into screening nor meeting all eligibility criteria does not guarantee enrollment into the study. To manage the total study enrollment, VH/GSK at its sole discretion, may suspend screening and/or enrollment at any site or study-wide at any time.

Participants are eligible to be included in the study only if all the following criteria apply:

Age

- Participant must be 18 to 65 years of age inclusive at the time of signing the informed consent.

Type of Participant and Disease Characteristics

2. Participants who are overtly healthy (other than HIV-1 infection) as determined by the investigator or medically qualified designee based on a medical evaluation including medical history, physical examination, laboratory tests, and cardiac monitoring.
3. Screening CD4+ T-cell count ≥ 200 cells/ μ L.

- 4. Documented HIV-1 infection and Screening plasma HIV-1 RNA $\geq 3,000$ copies/mL. A single repeat of this test is allowed within a single Screening period to determine eligibility.
- 5. Treatment-naïve: Defined as no ARVs (in combination or monotherapy) received after the diagnosis of HIV-1 infection. Prior use of oral PreP is permitted and meets inclusion. Prior use of parenteral PreP is exclusionary.

Weight

- 6. Body weight ≥ 50.0 kg (110 lbs) for men and ≥ 45.0 kg (99 lbs) for women and body mass index (BMI) within the range 18.5-31.0 kg/m² (inclusive - applies to males and females).

Sex and Contraceptive/Barrier Requirements

- 7. All participants participating in the study should be counseled on safer sexual practices including the use and benefit/risk of effective barrier methods (e.g. male condom) and on the risk of HIV transmission to an uninfected partner.

Participants Male at birth: There are no contraceptive requirements for participants who were male at birth.

Participants Female at birth: A participant who was female at birth is eligible to participate if they are not pregnant and not breastfeeding. Participant of childbearing potential (POCBP) must be using acceptable forms of birth control through to Day 39. The investigator is responsible for review of medical history, menstrual history, and recent sexual activity to decrease the risk for inclusion of a POCBP with an early undetected pregnancy. Refer to Section 10.4 for more details.

Informed Consent

- 8. Capable of giving signed informed consent, which includes compliance with the requirements and restrictions listed in the ICF and stated in this protocol.

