5.2. Exclusion Criteria

Participants are excluded from the study if any of the following criteria apply:

MEDICAL CONDITIONS

1. Women who are breastfeeding or plan to become pregnant or breast feed during the study.
2. Participants with acute HIV infection, evidenced by acute retroviral syndrome (e.g., fever, malaise, fatigue, etc.) and/or evidence of recent (within 3 months) documented viremia without antibody production and/or evidence of recent (within 3 months) documented seroconversion.
3. Any evidence of an active Centers for Disease Control and Prevention (CDC) Stage 3 disease [CDC, 2014], except cutaneous Kaposi's sarcoma not requiring systemic therapy during the study. Refer to Section 10.8 for more details.
4. Untreated syphilis infection [positive rapid plasma reagin (RPR) at screen] without documentation of treatment. Participants who have successfully completed treatment at least 7 days prior to Day 1 are eligible if recruitment is open.
5. Ongoing malignancy other than cutaneous Kaposi's sarcoma, basal cell carcinoma, or resected, non-invasive cutaneous squamous cell carcinoma, or cervical, anal or penile intraepithelial neoplasia; or other localized malignancies require agreement between the investigator and the study VH medical monitor for inclusion of the participant prior to randomization.
6. Treatment with immunomodulating agents (such as systemic corticosteroids, interleukins, interferons) or any agent with known anti-HIV activity (such as hydroxyurea or foscarnet) within 30 days of study drug administration.
7. Any pre-existing physical or mental condition which, in the opinion of the investigator, may interfere with the participant's ability to comply with the dosing schedule and/or protocol evaluations or which may compromise the safety of the participant; Any pre-existing physical or other psychiatric condition (including alcohol or drug abuse), which, in the opinion of the investigator (with or without psychiatric evaluation), could interfere with the participant's ability to comply with the dosing schedule and protocol evaluations or which might compromise the safety of the participant.

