4.2.2. Main analytical approach

The primary efficacy analysis will be based on the Full Analysis Set.

Maximum change from baseline in plasma HIV-1 RNA during monotherapy will be summarized in original and log10 scale using descriptive statistics as described in Section 4.1.1.

Any missing HIV-1 RNA data (e.g., due to missed visits in the clinic, LFU or for any other reason) will not be imputed and will remain missing. Whatever HIV-1 RNA data are available for a participant during monotherapy and prior to starting SoC will be used to calculate maximum VLD.

Participants who withdraw from study prior to the end of monotherapy period, preventing assessment of primary endpoint, no imputation will be performed for missed assessments after their study withdrawal.

All HIV-1 RNA data from all participants will be included in a listing.

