6.1.1. Participant Disposition

A summary of the number and percentage of participants who enrolled or failed screening will be provided. For screen failures, number and percentage of participants overall and by screen failure reason will be also provided.

A summary of the number and percentage of participants who entered, completed, are ongoing or withdrew from study at each study period (i.e. Monotherapy, Follow-Up) will be provided. A participant will be considered to have completed the Monotherapy period if has completed Day 11 visit and has not started SoC prior to Day 11. If a participant has started SoC treatment prior to Day 11 visit and has performed Day 11 visit, he/she will be classified as 'Not Completed' the Monotherapy phase. A participant is considered to have entered the Follow-Up period if there is a recorded concomitant antiretroviral treatment start date.

A summary of the number and percentage of participants who completed the study as well as those who prematurely withdrew from study will be provided. Reasons for study withdrawal will be summarized. A participant is considered to have completed the study if he/she has a "Completed" status in the Study Conclusion eCRF page.

For treatment arms where more than one study treatment administration is used during the monotherapy period (e.g. in Part 1b), a summary of study intervention status will be provided. This display will show the number and percentage of participants who have completed the scheduled study intervention or have discontinued study intervention prematurely, as well as primary reasons for discontinuation of study intervention.

The number and percentage of participants who withdrew from study due to an AE will be summarised by the outcome (fatal versus non-fatal) of the AE.

A listing of reasons for study treatment discontinuation and a listing of reasons for study withdrawal will be provided.

Subject-level disposition information will be available via [\[REDACTED\]](#).

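### The primary estimand's two stated interests are not reconciled for a non-SoC drug with anti-HIV activity, so HIV-1 RNA measured after such a drug stays in the primary nadir

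*SAP*

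**What the plan says.** The primary estimand (Protocol Section 3; SAP 1.1.1, Table 1) handles two kinds of extra medication before Day 11.

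- **Prohibited medication** gets a treatment-policy strategy: "any HIV-1 RNA data available after use of prohibited medication will be used in calculation of max VLD".
- **Early SoC** gets a while on-treatment strategy: "HIV-1 RNA collected after initiation of SoC, if for any reason this takes place prior to Day 11 will be excluded". SoC here means the open-label combination therapy that the investigator chooses, planned for the end of the Day 11 visit.

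The rationale has two limbs. The first reads "Interest is in evaluating efficacy irrespective of study treatment discontinuation or missed/incorrect doses, or use of prohibited medications". The second says that "interest is to evaluate efficacy of VH4004280/VH4011499 monotherapy and not in combination with other antiretroviral medication".

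The rest of the SAP follows the SoC trigger. Section 4.2.1 drops values after SoC initiation. Section 4.2.2 says "Whatever HIV-1 RNA data are available for a participant during monotherapy and prior to starting SoC will be used to calculate maximum VLD". Section 6.2.2 ends the monotherapy period at the start of SoC. The disposition section, 6.1.1, uses another trigger for one of its counts: "A participant is considered to have entered the Follow-Up period if there is a recorded concomitant antiretroviral treatment start date".

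The protocol recognises non-SoC drugs with activity against HIV, but in the visible text only at entry. Exclusion criterion 6 covers "any agent with known anti-HIV activity (such as hydroxyurea or foscarnet) within 30 days of study drug administration". Inclusion criterion 5 adds that "Prior use of oral PreP is permitted and meets inclusion".

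**The concern.** A drug that is active against HIV but is not SoC falls between the two rules. The first limb of the rationale keeps RNA measured after it, and the second limb would remove that RNA. No visible sentence says which limb takes precedence, and the operative rules keep the values.

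The primary endpoint is the change at nadir. A single value lowered by another drug becomes that participant's result if it falls below all of that participant's unaffected values. In a capsid inhibitor arm this overstates the effect. In a placebo group it creates a decline that is not natural variation and narrows the contrast with active treatment. The groups are very small, and selected outputs also feed the interim analyses that inform whether Part 2 runs and at what dose.

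**Working it through.** The plan states no figure on this point, so the check is mainly of the text. The sizes at the end are illustrations.

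**1. What each rule does with RNA taken after the drug (Day 1 to Day 11)**

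| Drug taken | Event in SAP Table 1 | Later RNA | First limb | Second limb |
|---|---|---|---|---|
| SoC started early | SoC before Day 11 | removed | not addressed | remove |
| Prohibited, no anti-HIV activity | prohibited medication | kept | keep | not addressed |
| Prohibited, anti-HIV activity, not SoC | prohibited medication | kept | keep | remove |
| Not on the prohibited list, anti-HIV activity, not SoC | none; SAP 4.2.2 applies | kept | not addressed | remove |

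The second limb is read here as covering any agent with anti-HIV activity. The limbs collide in row 3. In row 4 only the second limb speaks, and the rule goes against it. The prohibited-medication text in Protocol 6.9 is largely blacked out, so we cannot tell which row a given drug is in. The values are kept in both.

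**2. Which trigger applies**

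SAP 4.2.1, 4.2.2 and 6.2.2 use SoC start. SAP 6.1.1 uses SoC start to decide who completed monotherapy, but any recorded concomitant antiretroviral start to decide who entered Follow-Up. The broader trigger may show what was intended, but it governs a disposition count and not the endpoint.

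**3. Direction**

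Let A be a participant's RNA values before the other drug and B those after it. Then min(A and B together) ≤ min(A). Keeping B therefore leaves the decline unchanged or makes it larger, and never makes it smaller.

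**4. Size**

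Inputs from the documents:
- 6 participants per active arm and 2 placebo per compound in Part 1
- 1 further placebo per compound if Part 2 runs
- 4 per active arm and 1 placebo at each interim

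The input d, the extra deepening of one participant's nadir, is an assumption: 0.5 to 1.0 log10. The shift in the group mean is d/n.

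| Group | n | d = 0.5 | d = 1.0 |
|---|---|---|---|
| Active, final | 6 | 0.5/6 = 0.083 | 1.0/6 = 0.167 |
| Active, interim | 4 | 0.125 | 0.25 |
| Placebo, Part 1 | 2 | 0.25 | 0.50 |
| Placebo, Parts 1 and 2 combined | 3 | 0.167 | 0.333 |
| Placebo, interim | 1 | 0.5 | 1.0 |

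**5. Against the precision of an active arm**

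The half-width of the 95% CI for n = 6 is t(0.975, 5) × SD/√6 = 1.05 × SD. The protocol's precision table is blacked out, so the SD is also assumed. For SD 0.2 to 0.5 the half-width is 0.21 to 0.52 log10. A shift of 0.083 is 0.40 to 0.16 of that half-width, and a shift of 0.167 is 0.79 to 0.32 of it. Under these assumptions one affected participant moves the mean noticeably, but by less than the sampling uncertainty.

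**The case against.** The case for leaving the text alone has real weight.

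- **The rule follows a stated interest.** A reader might infer that the plan flatly contradicts its own rationale. It does not. The first limb expressly supports treatment policy for prohibited medication, and the second is given as the reason for the SoC cut-off. What remains is an overlap that nobody has addressed.
- **SAP 6.1.1 may already give the intended rule.** A reader might infer that the SAP puts one participant in two study periods at once. Read with 6.2.2, however, 6.1.1 can mean that any recorded antiretroviral start is taken as SoC start. On that reading, oral PrEP tablets taken on study would end monotherapy and the gap shrinks to agents that are not antiretrovirals. This is plausible but not stated for the endpoint, and agents of the kind in exclusion 6 would still be uncovered.
- **The per-protocol (PP) analysis removes the case.** SAP 4.2.3 says that none of the listed intercurrent events can occur in the PP set, and prohibited medication is one of them. This stands where the drug counts as prohibited. If it does not, removal depends on the adjudicated deviations in criterion 08 or on criterion 06, which is blacked out. PP also drops the whole participant, including sound earlier values, and it is a sensitivity analysis.
- **The event is remote.** Treatment-naïve means no antiretrovirals after diagnosis, so the PrEP example needs someone who resumes it during a 10-day period with frequent visits and medication review. That is an inference, not something the documents report.
- **The size is assumed.** Doses aim at near-maximal decline (Protocol 4.3), so another drug may add little in an active arm. All RNA data and concomitant medications are listed, so a case would be visible.

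These points limit the importance of the finding. They do not protect the primary estimate on the Full Analysis Set (FAS).

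**Conclusion.** The point holds in a limited form. As written, the primary FAS analysis keeps HIV-1 RNA measured after a non-SoC drug with anti-HIV activity, and the rationale does not settle whether it should. Any distortion makes the decline look larger, in whichever group it occurs.

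For one affected participant and an assumed extra 0.5 to 1.0 log10, the mean moves by 0.08 to 0.17 in an active arm of 6 and by 0.25 to 0.50 in a placebo group of 2. The active-arm figure is smaller if decline is already near maximal. The event is probably rare, and no rate is given. The direction follows from the endpoint definition. The size rests wholly on the assumed deepening. The conclusion does not depend on the blacked-out text in Protocol 6.9.

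The documents do not support a claim that the primary result will be biased. They support only the statement that the rule leaves it unprotected in an uncommon case. The primary analysis is descriptive, so no error rate or power is affected. This is a minor correction.

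**What to change.** In SAP Table 1 and Protocol Section 3, widen the event now limited to SoC so that it reads: *use of SoC, or of any other antiretroviral or agent with known anti-HIV activity, before Day 11*. Keep its while on-treatment strategy. Limit the treatment-policy rule to other prohibited medication. Use the same trigger in SAP 4.2.1, 4.2.2 and 6.2.2, and align it with 6.1.1. If the intention was always to treat any antiretroviral start as SoC start, say so in these places; agents that are not antiretrovirals still need to be named.

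If the protocol is not amended, the change can be made in the SAP and recorded in its Section 4.9, since Protocol Section 9 lets the SAP prevail on methods.

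The cost is a wording change and a concomitant-medication flag, best set before unblinding. The downside is that an affected participant contributes fewer RNA visits, so that participant's nadir may be shallower than with the full window. The FAS estimate can therefore err slightly towards a smaller decline. The change concerns only which values enter the analysis and alters no clinical management.
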